5.1.11 Laboratory Assessments

5.1.11.1 Clinical Laboratory Tests

Blood and urine samples for laboratory tests will be collected at the timepoints specified in Appendix A.

Due to the limitations on the volume of blood collection that is considered to be acceptable in young children with very small total circulating blood volumes (see Section 5), the laboratory samples will be ranked in the order corresponding to the study objectives, as shown in Table 2. Only Tier 1 assessments are considered mandatory and all efforts should be made to collect these in all subjects. Samples for the Tier 2 and Tier 3 assessments will only be collected if the blood volume threshold for subject's weight, as well as the subject's clinical status, permit (see Section 5 for further details).

Table 2: Clinical Laboratory Tests, By Tier

Tier 1 (Mandatory)								
Complete Blood Count (CBC)/ Hematology:	White blood cell count, red blood cell count, hemoglobin, hematocrit, MCV, MCH, MCHC, platelet count, neutrophil, lymphocytes, monocytes, eosinophils, basophils, peripheral smear for examination of cell morphology							
Chemistry:	Glucose, urea nitrogen, creatinine, sodium, potassium, chloride, calcium, magnesium, inorganic phosphorus, total protein, lactate dehydrogenase							
Liver Function Tests:	AST/SGOT, ALT/SGPT, alkaline phosphatase, GGT, albumin, bilirubin (direct, indirect, total)							
Anti-drug Antibody:	Anti-sebelipase alfa antibody							
Urinalysis:	pH, glucose, ketones, blood, protein, nitrite, and leukocytes (microscopic examination will only be done if blood, nitrite and/or leukocytes are abnormal)							
Coagulation Studies:	PT (INR), aPTT Fecal occult blood ((screening; thereafter only if the preceding assessment was abnormal or if clinically indicated)							
DNA Sample (screening):	See Section 5.1.15							
LAL Enzyme Activity (screening):	See Section 5.1.16							
Tier 2 (Optional, based on blood vo	lume thresholds)							
Lipid Panel:	Total cholesterol, triglyceride, HDL, LDL							
Other Chemistry:	Ferritin, high sensitivity C reactive protein (hs-CRF)							
Tier 3 (Optional, based on blood volume thresholds)								
Pharmacokinetic Assessments	See Section 5.1.14							
Exploratory Biomarkers	See Section 5.1.13							

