8.1 General Considerations

All data will be presented in listings; summary tables and graphs will be provided, as appropriate. Unless otherwise noted, tabulations for efficacy endpoints will be presented for subjects in the Full Analysis Set (FAS). Descriptive summary statistics (n, mean, median, standard deviation, minimum and maximum) will be calculated for the continuous variables. Shift tables and/or frequencies and percentages will be produced for the categorical variables. When percentages are reported, the number of treated subjects will be used as the denominator, unless otherwise noted. As appropriate, 95% two-sided confidence intervals (CIs) will be calculated around the estimates based on the exact binomial distribution for binomial endpoints and the t-distribution for continuous endpoints.

Baseline will be defined as the last measurement prior to the first infusion of sebelipase alfa. (Note: For exploratory analyses, the first available measurement after initiation of treatment may be used as baseline if a pretreatment measurement is unavailable.) In order to facilitate comparison with literature, survival analyses will be presented with subject birth date as "time 0"; analyses of other endpoints over time will consider date of first dose as "time 0".

Details of the planned analyses and statistical methodologies will be provided in a separate Statistical Analysis Plan.

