8.7 Efficacy Analysis

Efficacy will be analyzed for the Full Analysis Set.

Survival will be analyzed as the proportion of subjects surviving to 12, 18, and 24 months of age. As a complementary analysis, Kaplan-Meier survival curves of survival since birth and survival since first dose of IMP will be presented. Median age at death will also be calculated. A Kaplan Meier estimate of median survival past first dose of IMP will be computed.

Estimated survival rates and median age at death derived from this study will be compared to rates/times reported in the literature, and will be discussed in conjunction with information derived from previous studies.

Anthropometric indicators of growth, standardized by age and gender in accordance with the methodology described by the WHO and using WHO growth charts will be listed by study time point as observed values and as changes from baseline. Change from baseline in anthropometric data will be provided as graphs, and also tabulated as continuous data. In addition, the percentages of subjects who meet criteria for underweight, stunting, and wasting will be tabulated for each timepoint.

Change and/or percent changes from baseline in AST, ALT, and serum ferritin will be presented graphically (and tabulated) for each evaluation timepoint.

A subject will be considered to have achieved transfusion-free hemoglobin normalization (TFHN) if the subject meets all of the following criteria:

- 1. Has two post-baseline measurements of hemoglobin at least 4 weeks apart that are both above the age-adjusted lower limit of normal (LLN)
- 2. Has no known additional measurements of hemoglobin that are below the age-adjusted LLN during the (minimum) 4-week period; and
- 3. Had no transfusions during the (minimum) 4-week period, and also no transfusions for 2 weeks prior to the first hemoglobin measurement in the (minimum) 4-week period

If all 3 criteria are met, the subject will be considered to have achieved TFHN on the date of the first hemoglobin assessment in the 4-week period. The proportion of subjects who achieve TFHN will be summarized and, if sufficient data are available, a summary of time to TFHN will be created.

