#### 5.1.1.4. Laboratory Assessments

Blood and urine samples for clinical laboratory tests will be collected at the time points indicated in the schedule of assessments. Table 2 lists the laboratory panels and associated tests to be performed on blood (or urine) samples. Note that not all tests are performed at the same time points due to limitations on blood volume collection that is considered acceptable in young children with very small total circulating blood volumes (see Section 5.1.11 of study protocol for further details).

A central laboratory will be responsible for the analysis of all laboratory tests.

Any identified laboratory abnormalities will be specified as CS (Clinically Significant) or NCS (Not-Clinically Significant) by the Investigator or designee. Clinically significant abnormality will be recorded as AEs.

Tier 1 (Mandatory)			
Complete Blood Count (CBC)/ Hematology:	White blood cell count, red blood cell count, hemoglobin, hematocrit, MCV, MCH, MCHC, platelet count, neutrophil, lymphocytes, monocytes, eosinophils, basophils, peripheral smear for examination of cell morphology		
Chemistry:	Glucose, urea nitrogen, creatinine, sodium, potassium, chloride, calcium, magnesium, inorganic phosphorus, total protein, lactate dehydrogenase		
Liver Function Tests:	AST/SGOT, ALT/SGPT, alkaline phosphatase, GGT, albumin, bilirubin (direct, indirect, total)		
Anti-drug Antibody:	Anti-sebelipase alfa antibody		
Urinalysis:	pH, glucose, ketones, blood, protein, nitrite, and leukocytes (microscopic examination will only be done if blood, nitrite and/or leukocytes are abnormal)		
Coagulation Studies:	PT (INR), aPTT Fecal occult blood (screening; thereafter only if the preceding assessment was abnormal or if clinically indicated)		
DNA Sample (screening):	See Section 5.1.15 of Study Protocol		
LAL Enzyme Activity (screening):	See Section 5.1.16 of Study Protocol		
Tier 2 (Optional, based on blood volume thresholds)			
Lipid Panel:	Total cholesterol, triglyceride, HDL, LDL		
Other Chemistry:	Ferritin, high sensitivity C reactive protein (hs-CRP)		
Tier 3 (Optional, based on blood volume thresholds)			
Pharmacokinetic Assessments	See Section 5.1.14 of Study Protocol		
Exploratory Biomarkers	See Section 5.1.13 of Study Protocol		

Table 2: Clinical Laboratory Tests, by Tier

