# 7. STATISTICAL ANALYSIS

The Alexion Biostatistics Department or designee will perform the statistical analysis of the data derived from this trial. The analysis will be performed using the SAS® Life Science Analytics Framework version 4.7.2 or higher.

No formal inferential statistical testing will be performed. As appropriate, 95% two-sided confidence intervals (CIs) will be calculated around the estimates based on the exact binomial distribution (Clopper-Pearson method) for binomial endpoints and the t-distribution for continuous endpoints. Confidence intervals, where presented, will be considered descriptive and will be provided to facilitate clinical review and interpretation.

All data collected in this study will be provided in subject data listings sorted by subject number; the dose of SBC-102 temporally associated with the data will be included on the listing. Summary tables and/or graphs will be presented for each endpoint, as appropriate to the data, by evaluation time point.

Unless otherwise noted, the following standard conventions will be used for creating descriptive summaries:

- Continuous numeric endpoints will be summarized by providing the number of subjects with non-missing data, the mean and standard deviation (SD) of the data, and the minimum, first quartile (Q1), median, third quartile (Q3), and maximum value. Mean, median values, Q1 and Q3 will be presented with one decimal point more than the original value, SD will be displayed with two decimal points more than the original value will have the same number of decimal points as the original value;
- For categorical endpoints, the number and percentage of subjects with each possible outcome will be displayed. The denominator for percentages will include subjects with missing data.

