#### 7.2.3. Analyses for Laboratory Tests

Observed measurements and changes from Baseline to each study time point in clinical laboratory data will be summarized.

Frequencies of abnormal values relative to the laboratory normal range and clinically significant abnormal values as well as shift tables showing the change from baseline to post-baseline relative to the normal range will be summarized, if sufficient data are available for analysis.

Spaghetti plots for actual, change from baseline, and percent change from baseline will be created for the following parameters: ALT; AST; GGT; total bilirubin; albumin; alkaline phosphatase; total cholesterol; LDL-C; non-HDL-C; HDL-C; triglycerides; hemoglobin; platelets; prothrombin time (PT[INR]); partial thromboplastin time (PTT [INR]); and serum ferritin.

Plots of mean absolute change and mean percent change over time with standard deviations as error bars may be prepared for the following:

- Liver biochemical parameters: ALT/AST, GGT, bilirubin, albumin, alkaline phosphatase
- Lipids: total cholesterol, LDL-C, non-HDL-C, HDL-C, triglycerides
- Other: Hemoglobin, platelets, PT/PTT, serum ferritin
- The number of subjects contributing to each mean value will be presented in each figure

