#### 7.2.4. Physical Examination

A summary of findings including liver size, spleen size, and lymphadenopathy at Screening and follow-up will be presented for baseline and each post-baseline visit.

Summaries of liver and spleen will include the percentage of subjects with palpable and non-palpable organ, the regularity (smooth or nodular), and the sensitivity (tender or non-tender). In addition, the abdominal circumference will be summarized as observed, change from baseline, and percent change from baseline.

Summaries of lymphadenopathy will include whether any lymphadenopathy is present (yes/no) and the presence/absence and tender/non-tender status of each of five specific regions: cephalic, cervical, clavicular, axillary and inguinal.

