#### 7.3.1.4. Anthropometric Parameters

Anthropometric indicators of growth will be plotted on standard growth curves. Z-scores and percentiles based on the age-gender standardized norms will be calculated in accordance with the methodology described by the WHO (subjects  $\leq 24$  months) or CDC (subjects > 24 months to 18 years) and using the growth charts relevant to the respective methodology. Summaries will include summaries of observed z-scores and percentiles at each visit and also the change from baseline and the percentage change from baseline (percentile data only). In addition, the percentages of subjects who meet criteria for underweight (<-2 standard deviations [SD] from the median for WFA), stunting (<-2 SD from the median for LFA/HFA), and wasting (<-2 SD from the median for WFL/WFH) will be tabulated for each time point.

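### By-visit percentages for growth status and palpable organs keep unassessed children in the denominator, so printed prevalence can fall without any recovery (minor)

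*SAP*

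**What the plan says.** Both documents set a default. Among its conventions for categorical endpoints, SAP section 7 states: "The denominator for percentages will include subjects with missing data". Protocol section 8.1 states: "When percentages are reported, the number of treated subjects will be used as the denominator, unless otherwise noted". The Full Analysis Set is every child who received any study drug (SAP 6.1), and missing data are in general not imputed (SAP 7.3.1).

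The SAP departs from the default in at least two places. Baseline ECG percentages are taken over children who have a baseline ECG (SAP 7.2.6). The Denver II shift table is taken over children with both a baseline and a later result (SAP 7.2.7).

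No departure is written for two tables repeated across visits:
- Growth status. SAP 7.3.1.4 plans "the percentages of subjects who meet criteria for underweight" and the matching figures for stunting and wasting. Protocol 8.7 says the same: "the percentages of subjects who meet criteria for underweight, stunting, and wasting will be tabulated for each timepoint".
- Physical examination. SAP 7.2.4 says "Summaries of liver and spleen will include the percentage of subjects with palpable and non-palpable organ", with lymphadenopathy, at baseline and each later visit.

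A third table is less definite. SAP 7.2.3 plans "Frequencies of abnormal values relative to the laboratory normal range and clinically significant abnormal values", if data suffice, but names neither a percentage nor a denominator.

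**The concern.** Keeping every treated child in the denominator is sound for a favourable outcome such as survival or transfusion-free hemoglobin normalization, because a missing child then counts as a failure. Underweight, stunting, wasting and a palpable organ are unfavourable states, and there the same rule counts a missing child as free of the problem. As children die, leave or miss visits, the percentage affected is pulled down although nobody has improved.

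This matters because growth status is a secondary endpoint (SAP 5.2.1), and physical findings are part of the primary safety assessment (SAP 5.1.1). Both are naturally read as trends across visits. The losses may also be selective: protocol 3.2.2.2 calls growth failure one of the main contributors to mortality, so the children lost may often be the underweight ones.

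**Working it through.** The plan states no figure that depends on this rule, so there is nothing to reproduce. What follows is an illustration.

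**Inputs.** N = 10 treated, the most expected (SAP 9.3). Baseline prevalence and the numbers of deaths, exits and samples are assumptions, because the documents give none.

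**General formula.** With m children not assessed and a proportion p affected among those assessed, the printed figure is p(N − m)/N. It lies 100·p·m/N points below the assessed figure. At N = 10, each unassessed child costs 3 points if p = 30%, 5 if p = 50% and 8 if p = 80%.

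**Growth status.** Assume 8 of 10 underweight at baseline, no child changes status, and d underweight children die. Printed: (8 − d)/10. Assessed: (8 − d)/(10 − d).

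| d | Printed | Among assessed | Gap from denominator | Drift from 80% that remains |
|---|---|---|---|---|
| 1 | 7/10 = 70% | 7/9 = 77.8% | 7.8 | 2.2 |
| 2 | 6/10 = 60% | 6/8 = 75.0% | 15.0 | 5.0 |
| 3 | 5/10 = 50% | 5/7 = 71.4% | 21.4 | 8.6 |
| 4 | 4/10 = 40% | 4/6 = 66.7% | 26.7 | 13.3 |

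The last column is survivor selection, which a new denominator does not remove. The baseline percentage in the same surviving children does expose it: with no recovery it equals the assessed figure in every row (for example 4/6 at baseline and 4/6 at the visit).

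**Sensitivity to who is lost.** If losses are unrelated to weight, so that p stays at 80%, the expected printed figures for 1 to 4 losses are 72, 64, 56 and 48%. If the children lost are the two who were not underweight, the printed figure stays at 8/10 = 80%, while the assessed figure rises to 8/9 = 89% and then 8/8 = 100%. The artificial fall therefore needs some of the losses to be affected children.

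**Palpable liver.** Assume 10 of 10 palpable at baseline and no change. Losing 1 to 4 children prints (10 − d)/10 = 90, 80, 70 and 60%, against 100% of those examined.

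**Laboratory values, if percentages are printed.** Lipids and ferritin are Tier 2. Protocol 5.1.11.1 says "Samples for the Tier 2 and Tier 3 assessments will only be collected if the blood volume threshold" for the child's weight and clinical status permit, and SAP 5.1.1.4 adds "Note that not all tests are performed at the same time points due to limitations on blood volume collection". Suppose all 10 children are alive with abnormal ferritin, and 4, 6, 8 and then 10 are sampled. The printed figures are 40, 60, 80 and 100%, against 100% of those sampled throughout.

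**Adverse events by period.** Assume a constant 10% monthly risk, treatment to 36 months, and 10, 7, 6, 5, 4 and 3 children observed in windows of k = 3, 3, 6, 6, 6 and 12 months. The risk per window is 1 − 0.9^k = 27.1, 27.1, 46.9, 46.9, 46.9 and 71.8%. Multiplied by observed/10, the printed figures are 27.1, 19.0, 28.1, 23.4, 18.7 and 21.5%. Changing the denominator alone thus replaces a roughly flat series with a rise from 27% to 72% that reflects window length only. The rate is −ln(0.9) = 0.105 per patient-month in every window.

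**The case against.** The strongest reply is that the plan already shows enough to separate the cases. SAP section 7 displays the number and percentage for each possible outcome, and SAP 7.2.4 asks for both palpable and non-palpable percentages. If all 10 livers are palpable at baseline, four losses print 60% and 0%, while four recoveries print 60% and 40%. With 8 of 10 underweight, three deaths give 5 underweight and 2 not, while three recoveries give 5 and 5. The z-score summaries in SAP 7.3.1.4 carry the non-missing count, deaths and disposition are reported, and all data are listed. The rule is prespecified, consistent across both documents, and used in a single-arm descriptive study of up to 10 children.

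Most of this stands. A reader might infer that deaths and recoveries cannot be told apart in these tables. The documents do not support that wherever the complementary row is printed. What remains is that SAP 7.3.1.4 names only the children who meet the criteria, so a table shell could omit the complement, and the number assessed is not required for categorical tables.

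Two further limits are fair. The SAP does not say that a child who has died has missing data at later visits. That retention is implied by the protocol's all-treated denominator but not spelled out by visit. Also, a denominator of assessed children has its own selection bias, as the last column of the growth table shows.

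**Conclusion.** The point holds and is minor. For growth status and palpable organs, the stated default counts an unassessed child as unaffected, and no exception is written although the SAP writes them elsewhere. In the illustration the printed underweight figure is 8 to 27 points below the figure among assessed children for 1 to 4 underweight deaths. That size rests on N = 10, 8 underweight at baseline, no recovery, all deaths among underweight children, and the protocol's denominator applying to children who have died. The information can be recovered, but the headline percentage misleads.

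Three stronger readings go beyond the documents. First, that the abnormal-laboratory table is certainly affected: SAP 7.2.3 speaks only of frequencies, so this is an inference, and no sampling rate is given. Second, that adverse-event percentages by period need only a new denominator: the all-patient base is written for the system organ class and preferred term tables (SAP 7.2.2.2) and for treatment-emergent events generally (SAP 9.4.9.1), so its use by period is inferred, and the unequal windows are a separate problem. Third, that the survival proportions share the fault: deaths belong in that denominator, survival of children who discontinue is collected (protocol 4.6.2), and Kaplan-Meier curves with censoring counts are planned (SAP 7.3.1.1). How survival times are censored should be handled separately.

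**What to change.** - **SAP 7.3.1.4 and 7.2.4:** note an exception to the section 7 default. Use children assessed at the visit as the denominator, and print that number in each column.
- **Growth status:** add separate rows for children who have died and children alive or withdrawn but not assessed. Show beside each visit the baseline percentage in the same children, because survivor selection remains.
- **SAP 7.2.3:** if percentages of abnormal values are printed by visit, apply the same rule and print the number sampled. Tier 2 samples depend on weight and clinical status, so the children sampled may differ from the rest.
- **SAP 7.2.2.2, by-period table:** print the number under observation in each period and give events per patient-month. Do not rely on a changed percentage denominator alone.
- **Leave the default in place** for survival and transfusion-free hemoglobin normalization.

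The cost is SAP wording and table shells; no new data are needed. The drawback is that denominators vary between visits and periods, so they must be shown in every column.

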# 7.1. Study Subjects

#### 7.1.1. Disposition of Subjects

Subject disposition will be presented in a listing, and will include age, gender, date of consent, date and dose of first infusion of study drug, date and dose of last infusion of study drug, date of completion or premature discontinuation from the study, and reason for discontinuation if the subject discontinues prematurely. Data from all subjects who signed the informed consent will be included in the summary of subject disposition. The frequency and percentage of subjects who are treated in the study, completed the study, and discontinued from the study, along with reasons for discontinuation, will be summarized. In addition, the number of subjects in the FAS will be presented.

#### 7.1.2. Protocol Deviations

Major protocol deviations will be listed by subject. Protocol deviations will be identified by the study CRAs.

#### 7.1.3. Demographics and Medical History

All demographic and medical history information will be summarized using the FAS set.

#### 7.1.3.1. Demographics

The following demographic variables will be summarized:

- Age (months) reported to 1 decimal place (i.e. xx.x months)
- Sex
- Race
- Ethnicity

- Whether the subject is of Japanese descent and first, second, or third generation
- Birth weight (kg)

By-patient listings of demographic information will be produced.

#### 7.1.3.2. Disease Characteristics

The following disease characteristics will be summarized:

- Months since diagnosis
- Method of diagnosis (enzyme activity, genetic sequencing, other)
- Family members diagnosed with LAL-D (yes/no)

Further details of the family medical history, as well as details of the enzyme activity and genetic sequencing will be presented in the by subject listings.

